## SCHEMATIC OF STUDY DESIGN

A subject can be enrolled in this study from the angiographic confirmation of an LVO up to 45 days post-procedure. Assessments and imaging performed for this study are part of standard of care (SOC) for stroke treatment and screening can occur without obtaining consent. Informed consent is mandatory and must be obtained before any data is captured in the electronic Case Report Form (eCRF).

[figure not shown]

Figure 1 Schematic of Study Design

## 1. Background Information and Scientific Rationale

### 1.1. Background Information

According to the World Health Organization, 15 million people suffer from a stroke per year, leaving 5 million dead and 5 million severely disabled[1]. Approximately 90% of all strokes are Acute Ischemic Strokes (AIS), occurring when blood flow to the brain is blocked by a clot / thrombus [2]. The most severe AIS are due to Large Vessel Occlusions (LVO) and are associated with significant disability and mortality due to obstruction of the major vessels in the brain which include – Internal Carotid Artery (ICA), Middle Cerebral Artery (MCA), Vertebral Artery (VA), and the Basilar Artery (BA). Numerous studies have shown that removing the blood clot or occlusion can limit disability and drastically improve the patient's chances of having a good functional outcome.

### 1.2. Current Treatment Options

Intravenous Tissues Plasminogen Activator (IV t-PA) is routinely used to treat patients experiencing AIS in the United States, Europe and other regions. However, many patients do not meet the therapy's eligibility criteria. In the US, the FDA has approved IV t-PA in patients presenting up to 3 hours after symptom onset, while in the EU per ECASS (European Cooperative Acute Stroke Study) criteria, patients are eligible for IV t-PA up to 4.5 hours after symptom onset [3]. In addition to the time constraints, IV t-PA has shown to be less effective in recanalizing proximal LVOs [4]. Due to the limitations of IV t-PA, mechanical thrombectomy surfaced as a valuable alternative to effectively treat patients, regardless of IV t-PA eligibility[5].

Recent randomized controlled trials (SWIFT PRIME, ESCAPE, EXTEND IA, MRCLEAN, THERAPY) were successful in demonstrating the safety and effectiveness of thrombectomy with stent retrievers compared to IV-t-PA alone in treating AIS in patients with LVOs [6-10]. As a result, treatment guidelines have changed to include mechanical thrombectomy as part of standard of care (SOC) [11].

Advancement of catheter design and development has led to “A Direct Aspiration First Pass Technique” (ADAPT) that permits intracranial delivery of large-caliber aspiration catheters to the thrombus interface allowing for direct clot extraction. It was reported that ADAPT therapy is associated with similar reperfusion rates, clinical outcomes and complication rates compared with thrombectomy with stent retrievers [12].

A literature review involving 17 ADAPT studies and 5 Randomized Controlled Trials (ESCAPE, EXTEND, MRCLEAN, REVASCAT, and SWIFT PRIME) were successful in demonstrating higher rates of complete revascularization and reduced time from groin puncture to recanalization compared to standard methods – IV tPA and mechanical thrombectomy with stent retrievers[13].

Further, three randomized control trials compared endovascular approaches of aspiration vs stent retriever – ASTER, Penumbra Separator 3D and COMPASS. ASTER and Penumbra Separator 3D showed successful revascularization rates were similar between both techniques[14, 15]. COMPASS showed aspiration as first pass as non-inferior to stent retriever first line, on an intent to treat basis and showed a faster recanalization time [16]. These studies support the use of direct aspiration as an alternative to stent retriever as first line therapy for stroke thrombectomy[17].

### 1.3. Previous Experience with EMBOVAC™ Aspiration Catheter

No prior clinical investigations have been performed for the EMBOVAC™ Aspiration Catheter. Table 1 below provides an overview of the pre-clinical design verification and validation testing conducted on EMBOVAC™ Aspiration Catheter to demonstrate its safety and performance.

**Table 2 Pre-clinical Design Verification and Validation Testing**

Title	Description of Section
Design Verification Testing	Design Verification testing of the EMBOVAC™ Aspiration Catheter confirmed that the design outputs meet the design inputs.
Design Validation	Design Validation testing of the EMBOVAC™ Aspiration Catheter confirmed that the design outputs meet the customer requirements.
In-Vivo Animal Testing	
Fourteen Yorkshire pigs underwent a single interventional procedure on Day 0 in which selected arteries were treated with the Cerenovus EMBOVAC™ Aspiration Catheter and control device (SOFIA Plus) (16 devices each tested with clot, 12 each without clot). A minimum of 3 passes were performed in all vessels. Acute performance characteristics of the catheters were evaluated, including assessment of the preparation, compatibility between components, trackability, pushability, positioning, radiopacity and withdrawal. On Days 3 and Day 30, histologic evaluation was used to assess local tissue response and downstream organ/tissue effects.
 
This study demonstrated that the Cerenovus EMBOVAC™ Aspiration Catheter performed comparably to the control device (SOFIA Plus) with respect to handling, positioning, and pushability; and better with respect to R HV/microcatheter compatibility, and trackability. Clot was retrieved in

	100% of the Cerenovus Aspiration Catheter arteries and TICI 3 was achieved in 81% of those arteries after the third pass, comparably to SOFIA Plus. There were no dissections or perforations in the treated vessels. Vasospasm was a persistent observation which is typical in the swine model and not specific to the either the test or control devices. There were no health or clinical problems associated with the treatments and all animals survived to their scheduled end point.
Biocompatibility	The results of biocompatibility testing of the EMBOVAC™ Aspiration Catheter have demonstrated biocompatibility in compliance with applicable sections of EN ISO 10993.
Sterilization	Sterilization/microbiology validation testing of the EMBOVAC™ Aspiration Catheter was completed to demonstrate sterilization to a $10^{-6}$ Sterility Assurance Level (SAL).
Packaging	Packaging and labeling, conforms to defined customer requirements and patient needs.

### 1.3.1. Rationale

This study aims to assess the performance of the EMBOVAC™ Aspiration Catheter when used by multiple interventionalists and centers in a real-world clinical setting, as well as to explore the benefit of a ‘system approach’ using the Cerenovus products which have been designed for use together in the treatment of acute ischemic stroke (e.g., distal access catheter, balloon guide catheter). This study will also look at association between clot composition and reperfusion in order to gain better insight into the etiology of the disease and means for effective clot removal.

### 1.4. Commercial Product

The EMBOVAC™ Aspiration Catheter is commercially available in the EU since 2019. Please refer to the Instructions for Use (IFU) for instructions on use of the device.

### 1.5. Potential Risks and Benefits

#### 1.5.1. Known Potential Risks

Risks that may be associated with the use of the EMBOVAC™ Aspiration Catheter can be found in the commercially available IFUs found with the device.

### **1.5.2. Minimization of Risk**

EMBOVAC™ Aspiration Catheter must only be used by investigators who have received appropriate training in interventional neuroradiology and the treatment of ischemic stroke.

Efforts will be made to minimize the potential risks of the study through the following:

1. Investigators who participate in the study will be experienced with EMBOVAC™ Aspiration Catheter and will have performed a minimum of 2 cases with the device using ADAPT prior to study enrollment.
2. The site will have adequate resources to conduct the clinical study.
3. The study has been designed to ensure treatment and follow-up of subjects are consistent with current SOC.
4. The investigator and study personnel will be trained on the study protocol.
5. Each investigator will ensure oversight and approval of the study by the EC prior to activation of the study at the investigation site. Subject status will be monitored by the investigator or designee throughout the follow-up period as defined in the study protocol.
6. A CEC will review and adjudicate safety endpoints, as defined in CEC charter, throughout the course of the study.

### **1.5.3. Known Potential Benefits**

Although there may be no direct benefits of study participation, subject participants records will undergo an enhanced level of clinical scrutiny compared to routine SOC, which may provide some indirect health benefits. The potential benefits in this study of the commercially approved device outweigh any anticipated risks.

The results of the study may be beneficial to the research and medical community. The information learnt from this study may improve treatment to patients who require treatment for acute ischemic stroke in the future.

## **2. Objectives and Purpose**

### **2.1. Objectives**

The primary objective of this post-market clinical follow-up (PMCF) study is to characterize the performance of the EMBOVAC™ Aspiration Catheter in the treatment of acute ischemic stroke in a real-world clinical setting, as well as to confirm the benefits of a “system approach” using the Cerenovus products which have been designed for the use together in the treatment of acute ischemic stroke (e.g., distal access catheter, balloon guide catheter).

### 3. Study Design and Endpoints

#### 3.1. Description of the Study Design

This is a prospective, multi-center, single-arm, post-market clinical follow-up study that will enroll approximately 100 subjects at approximately 10 sites primarily in Europe, with clot collection for follow-on histopathological analysis. Subjects will be included in the study for a period of 3 months after the procedure, including follow up visits at 24 hours, 7 days (or discharge) and 90 days after the procedure.

#### 3.2. Study Endpoints

##### 3.2.1. Primary Endpoint

**Successful Revascularization (final mTICI  $\geq$  2b)** – Proportion of subjects with substantial angiographic reperfusion assessed using the modified Thrombolysis in Cerebrovascular Infarction (mTICI) scale at the end of the procedure. Successful achievement of the endpoint is defined as achieving a final mTICI score of 2b or greater in the target vessel as determined by the independent Imaging Core Lab.

##### 3.2.2. Secondary Effectiveness Endpoints

1. **Successful Revascularization (final mTICI  $\geq$  2b) without rescue therapy, as determined by Core Lab** – Successful achievement of the endpoint is defined as achieving a final mTICI score of 2b or greater in the target vessel as determined by the independent Imaging Core Lab without use of rescue therapy.
2. **Complete Revascularization (final mTICI  $\geq$  2c), as determined by Core Lab** – Successful achievement of the endpoint is defined as achieving a final mTICI score of 2c or greater in the target vessel as determined by the independent Imaging Core Lab.
3. **First Pass Effect (mTICI  $\geq$  2c without rescue), as determined by Core Lab** – Subjects with complete angiographic reperfusion defined as mTICI of 2c or greater after the first pass with the EMBOVACTM Aspiration Catheter as determined by the independent Imaging Core Lab without use of rescue therapy.
4. **Modified First Pass Effect (mTICI  $\geq$  2b), as determined by Core Lab** – Subjects with complete angiographic reperfusion defined as mTICI of 2b or greater after the first pass with the EMBOVACTM Aspiration Catheter as determined by the independent Imaging Core Lab.

5. **Time to recanalization (Time from arterial puncture to complete recanalization mTICI  $\geq$  2b), as determined by Core Lab** – as the time from arterial puncture to achievement of the first mTICI score of 2b or greater, or visualization of final angiographic result if an mTICI score of 2b or greater is not achieved, as determined by the independent Imaging Core Lab.
6. **Modified Rankin Scale (mRS) of 0 - 2 at 90 days** - Must be performed by a qualified independent evaluator. Whenever possible, mRS should be recorded at the follow-up clinic visit. If not possible, then a telephone assessment may be used.

### 3.2.3. Safety Endpoints

1. **Device related serious adverse events within 90 days** –where the EMBOVAC™ Aspiration Catheter caused, or cannot be ruled out as having caused, an event that has resulted in any of the consequences characteristic of an SAE. Device relatedness will be adjudicated by an independent CEC.
2. **Symptomatic Intracerebral Hemorrhage (sICH) at 24 hours specified according to the Heidelberg Bleeding Classification** – adjudicated by an independent CEC - defined as a new intracranial hemorrhage as detected by brain imaging, measured 24 hours after intervention [18], associated with any of the following:
  - $\geq 4$  points total NIHSS at the time of diagnosis compared to immediately before worsening. Note that a 4 points change is not compared with the baseline admission NIHSS score but instead to the immediate pre-deterioration neurological status
  - $\geq 2$  point in one NIHSS category. The rationale for this is to capture new hemorrhages that produce new neurological symptoms, making them clearly symptomatic but not causing worsening in the original stroke territory. For example, a new remote hemorrhage in the contralateral occipital lobe may cause new hemianopia that is clearly symptomatic, but the subject will not have worsening of  $\geq 4$  points on the NIHSS score
  - Leading to intubation/hemicraniectomy/EVD placement or other major medical/surgical intervention
  - Absence of alternative explanation for deterioration
3. **NIHSS at 24 hours post procedure** – NIHSS will be measured at 24 hours and compared to the baseline score.
4. **90 Day All-Cause Mortality** – All mortality regardless of cause at 90 days post-procedure.

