### **10.6. Measures to Minimize Bias**

Cerenovus will be diligent in controlling for bias by utilizing proper study design and implementation of the approved study protocol. EC approval will be obtained at all clinical sites prior to study initiation. Study agreements/contracts will be made with the hospitals/universities and all compensation for conduct of the study will be paid to the hospitals/universities and not to the investigators. Inclusion and exclusion criteria will be implemented to avoid selection bias.

An independent Clinical Events Committee (CEC) will review and adjudicate the safety endpoints, as specified in the CEC charter. CEC members will provide an impartial review and will not hold a financial interest in Cerenovus. An independent core laboratory will perform the angiographic assessments for the primary and secondary effectiveness

endpoints. These evaluations will be performed by an independent reader who does not hold a financial interest in Cerenovus.

Clinical outcomes will be measured in a standardized manner using the National Institutes of Health Stroke Scale, a standardized, objective, clinical assessment tool used to quantify and document the neurological status of patients and to act as a predictor for clinical outcomes. It is used to determine stroke and the severity of stroke.

Clinical outcomes will be measured in a standardized manner using the Modified Rankin Scale, a commonly utilized seven-point scale measuring functional outcome and disability in patients with stroke. The mRS measures independence and dependence related to activities of daily living and can be used over time to determine recovery or regression. In this study, 90 day mRS evaluations will be conducted by an independent evaluator who is not part of the interventional treating team, the patient's direct clinical care or involved in data entry (e.g., neurologist CRNC).

An independent CEC will review and adjudicate safety endpoints to determine whether they meet protocol-specified criteria. CEC members will provide an impartial and standardized review of these safety events.

An independent Imaging Core Lab will perform the angiographic assessments for the primary effectiveness endpoint, as well as the secondary effectiveness endpoints that are based on imaging. The Imaging Core Lab will provide an impartial and standardized review of imaging outcomes.

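### The sICH definition lists the no-other-cause condition as one of four sufficient criteria, so applied literally it can only over-count sICH

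*Protocol*

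**What the plan says.** Protocol 3.2.3 (Safety Endpoints, item 2) names the Heidelberg Bleeding Classification (HBC) and then writes out its own definition. The entry condition is "defined as a new intracranial hemorrhage as detected by brain imaging, measured 24 hours after intervention". The connector is "associated with any of the following". Four bullets follow at the same level:

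- A: at least 4 "points total NIHSS at the time of diagnosis compared to immediately before worsening"
- B: at least 2 "point in one NIHSS category"
- C: "Leading to intubation/hemicraniectomy/EVD placement or other major medical/surgical intervention"
- D: "Absence of alternative explanation for deterioration"

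Bullet B carries its own rationale, which is to catch "hemorrhages that produce new neurological symptoms, making them clearly symptomatic".

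Protocol 10.6 has the independent Clinical Events Committee (CEC) "adjudicate safety endpoints to determine whether they meet protocol-specified criteria". Protocol 1.5.2 and another paragraph of 10.6 point to the CEC charter. Protocol 10.5.4.2.2 and SAP 7.5.2.2 say only that sICH is assessed as HBC specifies. Neither restates how the four items combine. Under SAP 7.5.2 and 7.5.2.2 the result is a count, a percentage and an exact 95% interval in the safety analysis set.

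**The concern.** Bullets A to C say how severe the consequence of a bleed must be. Bullet D says nothing about severity. It refers to a deterioration that it does not itself define and asks whether something else accounts for it. That is the form of a condition attached to the other bullets, yet the list structure makes it a fourth way in.

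Read literally, this undermines the thresholds. Any new bleed with an unexplained deterioration, however small, already counts through D. The thresholds in A to C then decide the outcome only for patients whose worsening does have another explanation, which can hardly be the purpose of setting them.

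sICH is the only hemorrhage endpoint among the four safety endpoints. The study has one arm and no hypothesis test, so the reported rate and its interval are the whole result. Interim descriptive results also go into regulatory submissions (Protocol 10.5.7, SAP 7.9). If adjudicators follow the text, quietly correct it, or differ among themselves, the reported rate may not match the definition that readers take it to follow.

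**Working it through.** The plan states no sICH rate, so there is no figure to reproduce. The check is of the logic first and of scale second.

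**Step 1. The two rules.** Let H be a new intracranial hemorrhage on imaging, and A to D the bullets above.

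- As written: H AND (A OR B OR C OR D)
- With D as a required qualifier: H AND (A OR B OR C) AND D

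**Step 2. Every combination.** Five yes/no items give 2^5 = 32 combinations, of which 16 have H true.

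- As written, all of these 16 count except the one with A to D all false: 15 counted.
- With D required, D must be true and at least one of A, B, C true: 2^3 − 1 = 7 counted.
- Difference: 15 − 7 = 8. All 8 go from counted to not counted, and none goes the other way.

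The 8 combinations fall into two routes:

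| Route | Combinations | What is counted as sICH |
|---|---|---|
| D true, none of A to C | 1 | a deterioration below every threshold, with no other explanation |
| D false, at least one of A to C | 7 | a threshold met, but the worsening has another explanation |

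Combinations are not patients, so 8 of 32 says nothing about frequency. It settles the direction only.

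**Step 3. Direction.** If H, at least one of A to C, and D all hold, the as-written rule is met too. The qualified set therefore lies inside the as-written set, and the literal rate is equal to or higher than the qualified rate.

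Bullet C's wording already implies that the bleed led to the intervention. The second route may therefore run mainly through A and B. That would shrink the route without changing its direction.

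**Step 4. Scale.** Exact (Clopper-Pearson) limits for x events in n subjects are the 2.5% point of Beta(x, n − x + 1) and the 97.5% point of Beta(x + 1, n − x). All counts are assumed: 5 true events, with 0, 3 or 5 extra. The n of 100 is the planned enrollment. The n of 95 is the figure in the plan's own precision calculation.

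| Events | n = 100 | n = 95 |
|---|---|---|
| 5 (no extra) | 5.0% (1.6 to 11.3) | 5.3% (1.7 to 11.9) |
| 8 (3 extra) | 8.0% (3.5 to 15.2) | 8.4% (3.7 to 15.9) |
| 10 (5 extra) | 10.0% (4.9 to 17.6) | 10.5% (5.2 to 18.5) |

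At n = 100 each extra event adds 1 percentage point, so 3 to 5 extra add 3 to 5 points.

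**The case against.** The best defense is that the literal text may never be applied. The endpoint is named after a published classification, Protocol 10.5.4.2.2 and SAP 7.5.2.2 defer to it, and the charter may set out the logic correctly. The word deterioration in bullet D, and the word symptomatic in the endpoint's name, would lead specialist adjudicators to treat D as a qualifier. This stands: the documents do not show that any event has been or will be misclassified. It would be too strong to infer from Protocol 10.6 that the written list is the only rule the CEC has. But if the charter does differ from the protocol, the protocol definition is the one that needs aligning.

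It can also be said that the documents never state outright that D must be joined by AND. That too stands. The case rests on the bullet's wording and on the redundancy it creates, and the cited classification could not be consulted. Bullet B's rationale gives some support, but it explains that bullet only and is not a requirement placed on the others.

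Finally, the consequence is limited. sICH is a descriptive secondary endpoint, no test or stopping rule depends on it, and the assumed intervals above overlap widely.

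A reader might infer that the faulty list causes errors in both directions, missing some true sICH while adding false ones. The documents do not support that, because every discrepancy between the two rules is an added event.

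**Conclusion.** The definition is wrong as written, in a limited way. It makes a causal qualifier sufficient alone and not required otherwise, and no section of the protocol or SAP repairs this. Followed literally, it can only raise the reported sICH rate, an error in the cautious direction for a safety endpoint.

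The size cannot be derived from the documents. With 5 true events assumed in 100 subjects, 3 to 5 extra would move the reported rate from 5% to between 8% and 10%. If no patient falls in either route, or the CEC already reads D as a qualifier, nothing changes.

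The conclusion rests on reading D as a qualifier. The text strongly suggests that reading, but the sponsor should confirm it.

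**What to change.** First, the sponsor should check its cited classification to confirm how the fourth item is meant to connect. If it is a qualifier, reword the definition as:

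- a new intracranial hemorrhage on imaging, AND
- at least one of: the total-NIHSS criterion, the single-category NIHSS criterion, the major-intervention criterion, AND
- no alternative explanation for the deterioration.

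Use this wording in Protocol 3.2.3 and the CEC charter. Add it to SAP 7.5.2.2, which at present only points to HBC.

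Re-check events already adjudicated. If D is confirmed as a qualifier, only events called sICH need review for this reason, since an event that fails the literal rule also fails the qualified one. If the sponsor instead confirms that D is a stand-alone criterion, it should say so explicitly, and hemorrhages called not symptomatic need review as well.

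The cost is a few lines of text, the ethics committee review that Protocol 11.2 requires for an amendment, and a short file review. Sample size, data collection and the analysis method do not change.
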